7.10 Patient Follow Up

Whilst patients remain on trial treatment they will be reviewed on day 1 of every cycle with assessments as per section 7.3. For patients still on AZD2014 treatment after 1 year treatment should be reviewed at least 3 monthly. Assessments should be as per local practice with a CT scan conducted every 3-4 months.

If the patient comes off treatment but has not progressed, they will be reviewed in clinic and with a contrast enhanced CT of the neck, chest, abdomen and pelvis every 3 months for a year from the start of therapy. If the patient has not progressed after 1 year, they will then be followed up in clinic as per local policy with a CT as per local practice or performed on suspicion of progression. Patients will have no specific trial follow up, but their registering physician will be contacted every 6 months to determine progression and survival data.

At progression, patients will then be followed up 6 monthly for survival data.

All patients will be followed up for a minimum of 1 year, after starting treatment or until death.

8. ADVERSE EVENT REPORTING

The collection and reporting of Adverse Events (AEs) will be in accordance with the Medicines for Human Use Clinical Trials Regulations 2004 and its subsequent amendments. Definitions of different types of AE are listed in Appendix 5. The Investigator should assess the seriousness and causality (relatedness) of all AEs experienced by the patient (this should be documented in the source data) with reference to the Investigator Brochure.

8.1 Reporting Requirements

8.1.1 Adverse Events

All medical occurrences which meet the definition of an AE (see Appendix 5 for definition) should be reported.

Please note this does not include abnormal laboratory findings. An abnormal laboratory value is only considered to be an AE if the abnormality:

- Results in early discontinuation from the study treatment and/or
- Requires study drug dose modification or interruption, any other therapeutic intervention, or is judged to be of significant clinical importance
- Is Hyperglycaemia of > 1 week or if the investigator considers the rise in glucose to be medically significant

If a laboratory abnormality is one component of a diagnosis or syndrome, then only the diagnosis or syndrome should be recorded.

Pre-existing events should only be classified as AEs if they worsen by at least one grade from screening.

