7.5.1 General dose modifications for toxicities

Dose reduction and discontinuation guidelines for haematologic and non-haematologic toxicities due to AZD2014 are shown in Table 2 and 3. Dose re-escalation is not permitted.

Table 2.	Dose modifications and discontinuation criteria for non-haematologic toxicities*

NCI CTCAE Toxicity Grade	Action
Grade 1, or 2	None
Grade 3 or 4 and/or clinically significant	
Expected manageable/reversible with dose reduction	Hold study drug until meets one of the criteria below:
Toxicity remains (despite dose interruption) grade 3 or 4 or is clinically significant > 14 days	Discontinue study drug
Toxicity lasts 14 days or less and resolves to grade 2 or less or is no longer clinically significant	Reduce dose level per Table 1 and restart once toxicity has resolved to grade 2 or less or is no longer clinically significant
Grade 3 or 4 and/or clinically significant	
Not expected to be manageable/reversible with dose reduction	Discontinue study drug
Recurrence of Grade 3	Reduce one more dose level is available (see table 1), or if not discontinue study drug. NB note option of continuous dosing schedule as mentioned in 7.5

 Table 2.
 Dose modifications and discontinuation criteria for non-haematologic toxicities*

NCI CTCAE Toxicity Grade Action	
Recurrence of Grade 3 cardiac event ^a	Discontinue study drug
Recurrence of Grade 4	Discontinue study drug

* If the below specific recommendations for stomatitis/oral mucositis, hyperglycaemia, ILD/pneumonitis, ECG-changes and rash disagree with table 2 please follow the below not recommendations not table 2.

	Table 3.	Dose modifications and discontinuation criteria for haematological toxicitie
--	----------	--

NCI CTCAE toxicity grade	Action
Thrombocytopenia	
Grade 1, 2 or 3 (without bleeding)	None
Grade 3 (with bleeding) or grade 4	Hold study drug until it meets one of the criteria below:
Toxicity remains (despite dose interruption) grade 3 (with on-going bleeding episodes) or 4 > 14 days	Discontinue study drug
Toxicity lasts 14 days or less and resolves to grade 2 or less	Reduce dose level per table 1 and restart once toxicity has resolved to grade 2 or less
Neutropenia (NB GCSF is permitted as per local p	olicy)
Grade 1, 2 or 3	None
Grade 4	Hold study drug until it meets one of the criteria below:
Toxicity remains (despite dose interruption and GCSF) grade 4 > 14 days	Discontinue study drug

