Toxicity lasts 14 days or less and resolves to grade 2 or less	Reduce dose level per table 1 and restart once toxicity has resolved to grade 2 or less or is no longer clinically significant

RBC transfusion is permissive and advised in the event of symptomatic anaemia or a haemoglobin falling below 80g/l. If anaemia occurs, an assessment of underlying causality should take place and non-IMP related causes considered.

Grade 4 neutropenia (neutrophil count < 0.5×10^{9} /l) should always be treated with GCSF according to local policy

Platelet transfusion should be used in the following situations:

- as treatment of a bleeding event with a platelet count $< 50 \times 10^{9}$ /l,
- platelets < 20×10^9 /l with concomitant infection
- platelets < 10×10^{9} /l in asymptomatic patients

If a toxicity is experienced for patients in the combination stage then the treating investigator should ascertain the causality of the toxicity to both IMPs:

- If at least possibly related to AZD2014 follow the dose modifications above.
- If related to rituximab, management and dose modifications of rituximab should be as per the local site or Investigators standard procedures.

Dose calculations for any weight changes should also be conducted as per local practice.

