7.5.2.4 Recommendations for Treatment of Hyperglycaemia

Treatment related findings of elevated blood glucose levels should be reported as AE (s) if they fulfil the CTCAE criteria and SAE(s) if meeting the SAE reporting criteria.

In general management of hyperglycaemia should be performed according to local standards at the discretion of the Investigator.Due to the predicted short half-life of AZD2014, only a short period of hyperglycaemia with insulin resistance is expected. Therefore early treatment with high doses of insulin/and or oral anti-diabetes medication should be carefully evaluated and blood sugars and hypokalemia monitored as per standard clinical practice.

If blood glucose levels are < 250 mg/dl (Grade 2), generally no medical treatment is required. Dietary modification may be initiated.

For ≥ Grade 3 hyperglycaemia, dose modifications are required see Section 7.5.1

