12.2 Analysis of Outcome Measures

- Best overall response will be reported as the number and proportion of patients in each response category, and overall, during the first 6 cycles of treatment. In addition, best response observed after 6 cycles until the end of the trial will be reported by category and overall.
- The number and proportion of patients experiencing toxicity, including haematological and nonhaematological toxicity, will be reported with 95% confidence intervals.
- Time to event outcomes will be assessed using the method of Kaplan and Meier with point estimates presented at 6, 12, 24 and 36 months with 95% confidence intervals along with median survival time and confidence intervals. A Kaplan meier plot will be produced.
- The mean maximum % decrease during the first 6 cycles of treatment and overall will be reported with 95% confidence intervals

The biomarker study and PET scan analysis at present are exploratory.

There is little data on the expression of mTOR pathway proteins in DLBCL so the aim is to define expression in biopsy samples taken at relapse (or within 3 months). In collaboration with AstraZeneca, we will assess the expression of these proteins (p-S6, p-AKT, and p-4E-BP1) by immunohistochemistry (IHC). These will be measured at relapse, at subsequent progression, and in any tissue obtained at further optimal biopsy at 15 days. This will be initially assessed in 8 patients, with the potential to expand the analysis dependent on response data. We will then seek to determine a cut off which best predicts response to AZD2014, if indeed there is any correlation. Appropriate

statistical models (e.g. area under the curve, logistic regression) will be used to determine the cut off as detailed in the Statistical Analysis Plan.

Other ethically approved research may be performed on these samples if agreed by the trial management group.

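### Sections 7.5.2.4 and 8.1.1 give conflicting AE reporting rules for hyperglycaemia; and if the 12.2 haematological rates come from AE forms, grade 1-3 neutropenia and non-bleeding thrombocytopenia will be under-counted

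*Protocol*

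**What the plan says.** **AE definition.** Section 8.1.1 of the protocol asks for all events meeting the AE definition, then restricts it: "Please note this does not include abnormal laboratory findings. An abnormal laboratory value is only considered to be an AE if the abnormality" satisfies a listed condition. The conditions are early discontinuation of treatment; a general one, "Requires study drug dose modification or interruption, any other therapeutic intervention, or is judged to be of significant clinical importance"; and, for hyperglycaemia, a duration of more than one week or an investigator's view that the rise is medically significant. Appendix 5 repeats this list, but only after a comment that counts abnormal laboratory findings among the signs that can be an AE.

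**Glucose.** Section 7.5.2.4 has its own rule: "Treatment related findings of elevated blood glucose levels should be reported as AE (s) if they fulfil the CTCAE criteria". It sets no minimum duration and asks for no judgement of significance. The same section expects any hyperglycaemia to be brief and says that values below 250 mg/dl (grade 2) generally need no drug treatment.

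**Cytopenias.** In Table 3 (section 7.5.1) the thrombocytopenia row that begins "Grade 1, 2 or 3 (without bleeding" carries no action, and neither does neutropenia of grade 1 to 3. Action starts for platelets at "Grade 3 (with bleeding) or grade 4" and for neutrophils at grade 4.

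**Analysis.** Section 12.2 promises the number and proportion of patients with toxicity, "including haematological and nonhaematological toxicity, will be reported with 95% confidence intervals". It gives no grade limit and no data source. Section 12.1.2 refers only to toxicities recorded on treatment under CTCAE v4.0. The only CTCAE recording route described is the AE form in 8.2.1.1. Full blood counts and glucose are, however, taken on a fixed schedule (7.3.1).

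**The concern.** Toxicity of the single agent, and additional toxicity with rituximab, are stated secondary objectives. Two things can distort the rates that answer them.

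First, a site that follows 7.5.2.4 and a site that follows 8.1.1 will record different events from the same glucose result. This is an instruction to sites, so a statistical analysis plan cannot repair it afterwards: an episode never entered as an AE is not in the AE data.

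Second, a laboratory value that triggers nothing is by default not an AE, and Table 3 asks for nothing over most of the grade 1-3 range for neutrophils and platelets. A haematological toxicity proportion built from AE forms would then count only part of what CTCAE grading of the blood counts would show, and its confidence interval would be centred on that reduced proportion. The part that is counted would also vary by site, because it depends on the investigator's judgement and on local GCSF policy.

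**Working it through.** The protocol gives no expected rate of cytopenia or hyperglycaemia, so it has no figure on this point to reproduce. The check is mainly a comparison of texts.

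**Step 1. Glucose: which episodes fall between the rules?** Take a treatment-related elevation that meets CTCAE.

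- Grade 3 or higher: 7.5.2.4 requires a dose modification, so the general condition in 8.1.1 is met. Both rules report it.
- Grade 1-2, longer than one week: both report it.
- Grade 1-2, one week or less, treated or judged significant: both report it.
- Grade 1-2, one week or less, untreated and not judged significant: 7.5.2.4 reports it, 8.1.1 and Appendix 5 do not.

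The conflict is confined to the last line, but that is the kind of episode 7.5.2.4 expects.

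**Step 2. Cytopenias: which need not reach an AE form?**

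| Finding | Action in the protocol | AE under 8.1.1? |
|---|---|---|
| Neutropenia grade 1-3 | None in Table 3; GCSF allowed by local policy | Only if GCSF or other action is given, or judged important |
| Neutropenia grade 4 | Hold, GCSF | Yes |
| Thrombocytopenia grade 1-2, or grade 3 without bleeding | None in Table 3 | Only if action is taken or judged important |
| Thrombocytopenia grade 3 with bleeding, or grade 4 | Hold | Yes |
| Thrombocytopenia grade 3 or higher after starting a vitamin K antagonist | Stop AZD2014 (7.8.2) | Yes |
| Anaemia | No row in Table 3; transfusion advice in 7.5.1 | Yes if transfused, or judged important |

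The gap is the first and third rows, less whatever investigators judge important or treat.

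**Step 3. Does the gap reach the formal safety rule?** Section 12.6 counts toxicities that cause a treatment delay or dose modification in the first two cycles (at most 5 among the first 15 patients and 9 among 30; at most 1 of 3 and 2 of 6 for the combination). Treating a delay as an interruption, any laboratory event of this kind meets the general condition in 8.1.1 and is an AE. The count is unchanged.

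**Step 4. Scale of the effect on 12.2, if AE forms are the source.** Reported rate = true rate × share captured. The share captured is at most 1, so the bias can only be downward. One uncounted patient moves the rate by 1/30 = 3.3 points in stage one and by 1/6 = 16.7 points in the combination stage.

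As an illustration on assumed values, suppose 12 of 30 patients truly have a haematological toxicity: 40%, exact (Clopper-Pearson) 95% interval 22.7% to 59.4%.

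- 75% captured: 12 × 0.75 = 9, 9/30 = 30% (14.7% to 49.4%)
- 50% captured: 12 × 0.50 = 6, 6/30 = 20% (7.7% to 38.6%)
- 25% captured: 12 × 0.25 = 3, 3/30 = 10% (2.1% to 26.5%)

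At 50% capture, a true 6/30 (20%) is reported as 3/30 (10%) and a true 18/30 (60%) as 9/30 (30%). If the rates come instead from grading the scheduled blood counts, the 8.1.1 restriction removes nothing.

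**The case against.** The strongest objection is that 12.2 names no source. Blood counts are taken whatever the AE status: at screening, days 1 and 15 of cycles 1-2, day 1 from cycle 3, end of treatment and 30 days. Choosing the dataset, the worst grade per patient and the table layout is ordinary material for a statistical analysis plan, which is not at hand. That stands, and it is why the cytopenia point is conditional. It does not reach the glucose conflict or the contradiction in Appendix 5, which are fixed in the protocol.

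A reader might infer that no grade 1-3 cytopenia will be recorded unless someone acts on it. The text does not support that. An untreated value still qualifies if the investigator regards it as clinically important; grade 3 thrombocytopenia with bleeding requires a hold; 7.8.2 adds the vitamin K antagonist case; anaemia is outside Table 3 altogether, and 7.5.1 says "RBC transfusion is permissive and advised in the event of symptomatic anaemia or a haemoglobin falling below 80g/l", which is an intervention. The judgement route narrows the gap, but it also makes the gap depend on the site.

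On glucose, section 1.2.3.2 lists hyperglycaemia among the most frequent AEs overall but says none had been reported so far on intermittent schedules, the type used here. The number of affected episodes may be small. The same section describes cell-count reductions as of low clinical relevance. Both observations limit the likely size; neither removes the contradiction.

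**Conclusion.** The reporting contradiction is established. Short, untreated grade 1-2 glucose elevations that are not judged significant are AEs under 7.5.2.4 and not under 8.1.1, and Appendix 5 says both that abnormal laboratory findings belong to the AE definition and that they do not.

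The haematological point holds on one condition. If the 12.2 rates are taken from AE forms, grade 1-3 neutropenia and non-bleeding grade 1-3 thrombocytopenia that prompt no action and are not judged important will be under-counted. The direction is downward. The size depends on site judgement and GCSF policy and cannot be derived from the protocol; the figures above rest on assumed true rates and capture shares.

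Two stronger readings are tempting and should not be drawn. One is that the published rates will certainly be too low: that needs the AE form to be the only source, which no section says. The other is that the tolerability decision is biased: an event that causes a delay or dose modification is already an AE, so 12.6 stands. What is at risk is the descriptive toxicity rates. The changes below should be made, because they are cheap and one of them cannot be made at the analysis stage.

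**What to change.** 1. Bring 7.5.2.4, 8.1.1 and Appendix 5 to a single AE reporting rule for hyperglycaemia and for laboratory findings generally, and remove the opposing statements in Appendix 5.
2. In 12.2, state that haematological and biochemical toxicity, glucose included, is graded by CTCAE v4.0 from the blood results already scheduled in 7.3.1, taking the worst grade per patient, and is tabulated separately from reported AEs. If the AE form is to remain the source, label those rates as clinically significant events only.

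The cost is wording in four places and some programming. No new tests and no change to patient management are needed. Reported toxicity rates may rise.

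The second change does not replace the first. The footnotes to the assessment table in 7.3 allow samples up to 3 days before the visit, so day 1 and day 15 samples will often fall at the end of the drug-free gap, and glucose is fasted at screening only. Scheduled samples will still miss some short glucose rises, so a single AE rule is needed as well.

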7. Male patients should be surgically sterile or willing to use barrier contraception (i.e. condoms) as described in the protocol, (different for patient receiving rituximab*)

8. Ability to swallow and retain oral medication

9. CT measurable disease with at least 1 lesion having long axis \geq 1.5cm or splenomegaly \geq 14cm in cranio-caudal length attributable to relapsed lymphoma

10. Patients must have negative virology for HIV.,

11. For patients receiving single agent AZD2014 treatment only :

- Hepatitis C serology must be negative
- Hepatitis B serology must not indicate active infection. Specifically:
- Patients who are hepatitis B surface antigen positive are excluded

Patients who are anti-hepatitis B sAg antibody positive in the absence of anti-core antibody are eligible if hepatitis B DNA is negative.

Patients who are positive for anti-hepatitis B core antibody (with no surface antigen) are eligible if hepatitis B DNA is negative.

12. For the rituximab cohort only:- Hepatitis C serology must be negative

- Hepatitis B surface antigen and anti-core antibody must be negative

- Patient with a history of vaccination to hepatitis B and who are positive for anti-hepatitis B sAg antibody but negative for anti-core antibody are eligible if hepatitis B DNA is negative

Exclusion Criteria

Patients must not enter the study if any of the following exclusion criteria are fulfilled:

 Prior chemotherapy, biological therapy, radiation therapy, androgens, thalidomide, immunotherapy, other anticancer agents, and any investigational agents within 21 days of registration (not including palliative radiotherapy at focal sites to non-target lesions). Corticosteroids are permitted during screening but should be weaned down to a maximum dose of prednisolone 10mg daily (or equivalent) by day 1 of cycle 1.

- With the exception of alopecia, any unresolved toxicities from prior chemotherapy should be no greater than CTCAE (Version 4.0) Grade 2 at the time of registration.

- 2. Major surgery within 4 weeks prior to entry to the study (excluding placement of vascular access), or minor surgery within 2 weeks of entry into the study.
- 3. Exposure to potent or moderate inhibitors or inducers of CYP3A4/5, Pgp (MDR1) and BCRP if taken within the stated washout periods before the first dose of study treatment. See Appendix 2.

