4.2 Exclusion Criteria

Patients must not enter the study if any of the following exclusion criteria are fulfilled:

 Prior chemotherapy, biological therapy, radiation therapy, androgens, thalidomide, immunotherapy, other anticancer agents, and any investigational agents within 21days of registration (not including palliative radiotherapy at focal sites to non-target lesions). Corticosteroids are permitted during screening but should be weaned down to a maximum dose of prednisolone 10mg daily (or equivalent) by day 1 of cycle 1.

- With the exception of alopecia, any unresolved toxicities from prior chemotherapy should be no greater than CTCAE (Version 4.0) Grade 2 at the time of registration.

- 2. Major surgery within 4 weeks prior to entry to the study (excluding placement of vascular access), or minor surgery within 2 weeks of entry into the study.
- 3. Exposure to potent or moderate inhibitors or inducers of CYP3A4/5, Pgp (MDR1) and BCRP if taken within the stated washout periods before the first dose of study treatment. See Appendix 2.
- 4. Exposure to sensitive or narrow therapeutic range substrates of the drug transporters Pgp (MDR1), BCRP, MATE 1, MATE 2K, OATP1B1 and OATP1B3, within the appropriate wash-out period (a minimum of 5 x the reported terminal elimination half-life of each drug) before the first dose of study treatment. See table in appendix 3.
- 5. Previous treatment with any first generation mTORC1 inhibitors (rapamycin, sirolimus, temsirolimus, everolimus) or any dual mTORC1/2 inhibitors (e.g. AZD2014, AZD8055).
- 6. Patients who have experienced intolerable AEs prejudged by the treating Investigator due to other mTORC1 or mTORC1/2 inhibitors, PI3 kinase inhibitors, or AKT inhibitors.
- 7. Patients with proven central nervous system (CNS) involvement.
- 8. As judged by the Investigator, any evidence of severe or uncontrolled systemic diseases (e.g., severe hepatic impairment, interstitial lung disease (e.g.bilateral, diffuse, parenchymal lung disease), uncontrolled chronic renal diseases (e.g. glomerulonephritis, nephritic syndrome, Fanconi Syndrome or Renal tubular acidosis) or current unstable or uncompensated respiratory or cardiac conditions, or uncontrolled hypertension, active bleeding diatheses or active infection. Screening for chronic conditions is not required.
- 9. Patients who have experienced any of the following procedures or conditions currently or in the preceding 12 months:

- coronary artery bypass graft

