5.1.1 Screening Assessments

All patients will be screened prior to registration. The following screening assessments will be performed within 28 days prior to trial entry unless stated otherwise (see section 7.3 for more details of the assessment):

- Demographic data
- Medical history (including prior diagnosis, treatment and any existing conditions)
- Height & Weight

Blood tests

- Full blood count and biochemistry (including glucose and if abnormal fasted glucose), Hba1c, triglycerides, cholesterol, Troponin (isoform as per institutional norm), serum creatinine, bilirubin, LDH and ALT/AST)
- Blood for virology. Patients must have negative virology for HIV and hepatitis C prior to trial entry. For stage one (AZD 2014 treatment only), hepatitis B serology must not indicate active infection. Prophylaxis is advised in patients who meet inclusion criteria 11 whilst being antihepatitis B sAg antibody positive and who are positive for anti-hepatitis B core antibody (with no surface antigen). Prophylaxis is not recommend for those with isolated anti-hepatitis B sAg and a history of vaccination.
- For stage 2 treatment (AZD 2014 with rituximab) Hepatitis B surface antigen and anti-core antibody must be negative.

Examinations/Tests

- Clinical assessment, including, vital signs (heart rate, systolic and diastolic BP, oxygen saturation (pulse oximetry), temperature, weight)
- ECOG performance status
- Assessment of constitutional symptoms -, night sweats, recurrent fever ≥38.0°C in the absence of infection, and history of weight loss.
- Urinalysis (test strip to include Haemoglobin, leukocytes, nitrite and proteins)
- Bone Marrow Trephine Biopsy (if indicated for disease staging)
- Pregnancy test for females of child-bearing potential (to be obtained prior to registration and within 7 days of starting therapy)
- Contraception review as per section 5.3 below

Radiology

• PET-CT (contrast enhanced CT component) Neck, Chest, Abdomen and Pelvis (NCAP) as per Torch PET manual. Contrast enhanced CT Neck, Chest, Abdomen and Pelvis (NCAP), can be performed at the same imaging session as the PET-CT if possible as per local practice. If performed at the same session, an unenhanced low dose CT should be performed

followed by a PET scan then a contrast enhanced CT NCAP so that accurate quantitation of PET data will be possible. A full inspiration breath-hold CT should be performed as part of the CT NCAP

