6. TRIAL ENTRY

Patients will be registered to the trial via the Cancer Research UK Clinical Trials Unit (CRCTU).

2:[name]

9am-5pm Monday to Friday

An eligibility checklist and registration form (found in the ISF) should be completed prior to registration by the Investigator or designee.

The patient trial number and treatment allocation will be given over the telephone, followed by a fax confirmation. Treatment should start within 7 days of registration.

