8.1.3 Reporting period

Details of all AEs (except those listed above) will be documented and reported from the date of commencement of protocol defined treatment until 30 days after the administration of the last treatment.

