8.2 Reporting Procedure

8.2.1 Site

8.2.1.1 Adverse Events

AEs should be reported on an AE Form (and where applicable on an SAE Form). An AE Form should be completed at each visit and returned to the Trials Office.

AEs will be reviewed using the CTCAE, version 4.0 (see Appendix 6). Any AEs experienced by the patient but not included in the CTCAE should be graded by an Investigator and recorded on the AE Form using a scale of (1) mild, (2) moderate or (3) severe.

For each sign/symptom, the highest grade observed since the last visit should be recorded.

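### Pre-existing adverse events are judged against a screening grade up to 35 days before first dose, so some worsening on AZD2014 is not an AE and some pre-dose worsening may be

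*Protocol*

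**What the plan says.** **Reference grade.** Protocol section 8.1.1 sets the rule for conditions present before treatment: "Pre-existing events should only be classified as AEs if they worsen by at least one grade from screening". Appendix 5 repeats it in the definition of an adverse event.

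**Age of that grade.** Section 5.1.1: "The following screening assessments will be performed within 28 days prior to trial entry unless stated otherwise". Section 6: "Treatment should start within 7 days of registration".

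**Limits tied to registration.** Exclusion criterion 1, in the synopsis and in 4.2, bars earlier treatment, including "other anticancer agents, and any investigational agents within 21 days of registration". It also requires that "any unresolved toxicities from prior chemotherapy should be no greater than CTCAE (Version 4.0) Grade 2 at the time of registration". Neither limit refers to the screening visit.

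**What is collected and reported.** Section 8.1.3 has AEs "reported from the date of commencement of protocol defined treatment until 30 days after the administration of the last treatment". Section 8.2.1.1 adds: "For each sign/symptom, the highest grade observed since the last visit should be recorded". Section 12.2 states the analysis: "The number and proportion of patients experiencing toxicity, including haematological and nonhaematological toxicity, will be reported with 95% confidence intervals".

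**ECG findings are treated differently.** Under 7.3.3 a clinically significant abnormality seen before the first dose is recorded as a concurrent condition. Only an abnormality that was absent before dosing becomes an AE.

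**The concern.** An AE count in a single-arm trial is read as what happened on the drug. For a patient who already has a symptom, that calls for a comparison with the state just before the first dose. The screening grade can differ from that state. Toxicity from earlier therapy may still be settling, disease may progress, and 4.2 has corticosteroids weaned by cycle 1 day 1. That this weaning could shift symptoms is an inference, not something the protocol says.

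If the patient improves between screening and day 1, the reference is too high and a real worsening on AZD2014 can go unrecorded. If the patient deteriorates, the reference is too low and a change that preceded the drug can enter the AE record. The two errors run in opposite directions, and nothing makes them cancel.

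Toxicity of the single agent is a secondary objective. Section 1.2.3.2 lists fatigue, mucositis, nausea and diarrhoea among the most frequent AZD2014 events, and patients may already have such symptoms at entry. Sites apply the rule when they decide what to record, so a later analysis cannot reliably recover what was left out.

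**Working it through.** **1. The plan's own figures.** The protocol gives no figure for the age of the reference grade. The nearest are the operating characteristics of the tolerability rule in 12.6: at least 10 of 15, then at least 21 of 30, with rates of 60% and 80%. With X1 and X2 each binomial on 15 patients:

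- Early stop at 60%: P(X1 ≤ 9) = 59.7% (stated 59.7%).
- Declared tolerable: sum over x = 10 to 15 of P(X1 = x) × P(X2 ≥ 21 − x). This gives 15.2% at a 60% rate (stated 15.3%) and 90.5% at 80% (stated 90.4%).

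The stated figures are reproduced to within 0.1 point.

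**2. Age of the reference.** Screening window (5.1.1) plus registration to first dose (section 6): 28 + 7 = 35 days at the outside.

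**3. Overlap with earlier therapy.** Screening window minus washout: 28 − 21 = 7 days. A screening assessment in the first week of the window can precede the last permitted earlier treatment.

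**4. The rule applied to grade sequences.** An AE needs an on-drug grade at least one above the reference.

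| Screening | Pre-dose day 1 | On AZD2014 | Against screening (as written) | Against pre-dose |
|---|---|---|---|---|
| 2 | 1 | 2 | 0: not an AE | +1: AE |
| 1 | 2 | 2 | +1: AE, if reported on treatment | 0: not an AE |
| 2 | 1 | 3 | +1: AE | +2: AE |
| 2 | 0 | 2 | not an AE if still called pre-existing; undefined | AE |

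The first row is the clear case. The symptom never resolved, so it is plainly pre-existing; it worsened on treatment; and it is not an AE. The third row shows that a return above the screening grade is still counted.

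**5. Weight of one misclassified patient.** In stage one, 1/30 = 3.3 percentage points on that symptom's proportion. In stage two, 1/6 = 16.7 points. The documents do not say how many patients would follow the first or second row.

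**6. Does it reach the tolerability rule?** Section 12.6 counts toxicities that lead to a delay or dose modification in the first two cycles. Table 2 in 7.5.1 generally ties such action to grade 3 or 4, or to clinical significance. Residual chemotherapy toxicity is at most grade 2 at registration, so a grade 3 or 4 event will normally exceed the reference. The exceptions are:

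- stomatitis, where 7.5.2.2 interrupts treatment from grade 2;
- lower grades judged clinically significant;
- a screening grade of 3 or more taken before recovery.

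**The case against.** The strongest reply is that the rule reaches less far than it first appears.

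- **Resolved events.** The rule covers pre-existing events only. A toxicity at grade 0 on day 1 has arguably ended, and a new episode on drug meets the general AE definition in Appendix 5. A reader might infer that every returning chemotherapy toxicity is lost. The text does not support that: the status of a resolved event that recurs is undefined, and a return above the screening grade is counted on any reading. What stands is an ambiguity to close.
- **Worsening before the first dose.** Reporting starts at first dose, 12.1.2 uses toxicities recorded during treatment, and section 8 requires a causality assessment for every AE. Pre-dose worsening therefore need not be attributed to AZD2014. This limits the second error without removing it: a symptom that persists after dosing still meets the one-grade test, and the highest-grade rule in 8.2.1.1 could bring a pre-dose grade onto the day 1 form.
- **Scope.** Laboratory abnormalities become AEs mainly through the action they prompt or their clinical importance, and ECG findings already use the pre-dose state. This stands.
- **Extremes.** The 35 days and the 7-day overlap are outer limits. Screening is a period and need not be a single early visit. This also stands, but the protocol does not say which screening grade is the reference.

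A reader might also infer that the tolerability decision is compromised. If a share m of intolerable outcomes went unseen, the apparent rate at a true 60% would be 1 − 0.4 × (1 − m). The risk of wrongly declaring the treatment tolerable would then rise from 15.2% to 20.9%, 27.7% or 44.3% for m = 5%, 10% or 20%. No value of m can be taken from the documents, and step 6 of the working shows why it should be small. These figures are an illustration, not a finding.

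**Conclusion.** The concern holds in a limited form. The screening reference misclassifies a pre-existing symptom that improves before cycle 1 day 1 and then worsens on treatment back to, but not above, its screening grade. It may also classify as an AE a symptom that worsened before dosing and merely persists. It is out of step with the protocol's own pre-dose reference for ECG findings and its first-dose start for AE reporting.

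The consequence is confined to the descriptive proportions in 12.2, mainly low-grade symptoms, on the assumption that those proportions are drawn from the AE forms. Assumed shares could be multiplied into a figure in percentage points, but the protocol supplies none of them, so no total bias is claimed. The sample size, the response threshold and the tolerability thresholds stand. The one loose end there is grade 2 stomatitis: a recurrence at its screening grade would interrupt treatment without being an AE, so its place in the tolerability count is unclear.

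**What to change.** In section 8.1.1 and in Appendix 5:

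1. Replace 'from screening' with 'from the last assessment before the first dose (cycle 1 day 1 pre-dose)'.
2. State that an event resolved before the first dose that recurs on treatment is a new AE.
3. Record the pre-dose cycle 1 day 1 grade of each pre-existing condition on the AE form. This should be the grade at that moment, so that the highest-grade rule in 8.2.1.1 does not replace it with an earlier peak.

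The cost is small. Clinical assessment and bloods on cycle 1 day 1 are already in the 7.3 schedule, and an AE form is completed at each visit. It is not wording alone, though: the assessments listed in 7.3.2 do not expressly include grading of symptoms such as mucositis or nausea, so step 3 adds one data item. If patients have been registered under the present wording, the report should say which reference applied to whom. No sample size or decision threshold changes.
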